Study Title: Evaluation of 19-gauge vs 21-gauge EBUS TBNA in assessing thoracic lymphadenopathy

NCT # NCT03657849

Participant Contact Narrative: Evaluation of 19-gauge vs 21-gauge EBUS TBNA in assessing thoracic lymphadenopathy

1. Summary:

Endobronchial ultrasound-guided transbronchial needle aspirate (EBUS-TBNA) is a technique used to take samples of body tissue inside the chest without having to undergo an operation. During this procedure, a special telescope (called a bronchoscope) is inserted through the mouth into the airways. Ultrasound technology allows the doctor to see the structures just outside the airway. By being able to see the structures outside the airway, the doctor is able to safely pass a fine needle through the airway to take samples of abnormal tissue.

EBUS-TBNA is used to take samples of tissue from the mediastinum. The mediastinum is the part of the chest between the lungs, and contains the heart, gullet, windpipe and lymph nodes. This area of the body is usually difficult to access without open surgery, hence the use of EBUS-TBNA. EBUS-TBNA may be used to investigate enlarged lymph nodes. This may be due to tuberculosis, sarcoidosis or cancer.

Currently, smaller 21-gauge and larger 19-gauge needles are used during the EBUS-TBNA procedure at Regions Hospital. The purpose of this study is to find out which needle is better in finding the explanation for the enlarged lymph nodes, minimizing complications and any follow up procedures that may be necessary if we are unable to get enough tissue during the EBUS-TBNA procedure (surgical sampling, radiological sampling, and/or follow-up imaging).

2. Study Aims:

Using the larger 19-gauge needle instead of 21-gauge needle during EBUS TBNA will have higher yield without increasing complications

Primary outcome:

- 19-gauge needle yield vs 21-gauge needle yield (true positive + true negative)/total

Secondary outcome:

- Number of adequate samples by rapid onsite evaluation (ROSE)
- cytology assessment of sample size
- adequacy for molecular testing for lung cancer

H1: 19-gauge needle will have at least 7% higher absolute yield than 21-gauge needle (current yield for 21-g needle is 83%)

3. Background, Rationale, Significance:

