This is a prospective, diagnostic accuracy study. For each lymph node sampled, we will alternate between the 19-g and the 21-g with each pass. Typically, an average of 5 passes is done in each lymph node (though number ranges from 3-12 based on physician judgment), for the study a minimum of 3 passes with each needle will be requested to provide adequate tissue for comparison. The choice of needle for the first pass will be randomized. More passes will be allowed with alternating needles based clinicians' judgment. Tissue obtained with the 19-g needles will be compared to tissue obtained with the 21-g needles with regards to diagnosis yield and adequacy for molecular testing.

b. Population:

i. Inclusion/Exclusion criteria

Inclusion:

- Age 18 years or older
- Able to provide informed consent
- Referred for EBUS TBNA sampling at Regions Hospital

Exclusion:

- On therapeutic warfarin, plavix or ticagrelor in the last 5 days

- INR >1.8, platelets <50K (evaluated at enrollment if patient has had them drawn as part of standard of care)
- ii. Sample size:

A total of 50 patients will be enrolled, with an average of 1.7 lymphnodes sampled in each patient. Patients will be a convenience sample of patients referred to have the EBUS-TBNA procedure at Regions Hospital during the study period.
- c. Data collection process
 - i. Process steps for identification of patients or records

All patients referred for EBUS TBNA sampling at Regions Hospital who meet the inclusion/exclusion criteria will be approached to be enrolled. These patients will be identified by one of the study investigators. Of note, the exclusion criteria for INR and platelets will have been drawn and evaluated as part of standard of care only, based on the concern for coagulopathy. These are not required to be drawn for study enrollment. All physicians who perform this procedure at Regions Hospital are listed as investigators on this study.
 - ii. Recruitment

Subjects will be identified based on referral for EBUS TBNA procedure at Regions Hospital by one of the study investigators. Because all physicians who perform the EBUS TBNA procedure at Regions are study investigators, one of the investigators will be aware of every patient referred to have this procedure. Upon becoming aware of a patient referred for this procedure, the study investigator will discuss the procedure with the patient.
 - iii. Consent

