The EBUS-TBNA procedure is done with both 19-g and 21-g needles as standard of care. The conduct of the procedure with both needle sizes in a systematic manner with concurrent data collection as described above is specific to the study. This procedure is conducted at Regions Hospital by the listed study investigators. The procedure typically takes between 20 and 90 minutes to complete, during which time the patient is under moderate sedation. During a standard procedure, the physician always performs at least four passes, sometimes more depending on the adequacy of the tissue being obtained. The average is 5.5 passes per lymph node. Participation in the study will likely result in an additional 1 to 2 total passes per patient. The randomization aspect of this study involves randomizing which needle size the physician starts with, with subsequent passes alternating between the two needle sizes. Initial needle size will be randomized using research randomizer. The randomization assignments for each study ID number will be kept in a document accessible by all investigators for use during enrollments. The investigators will not be blinded to the randomization assignment but the subjects will not be informed of which needle size they were assigned to start with.

e. Outcome/endpoint and other variable definitions, and instruments used

| Variable Name | Data Source | Purpose | Measurement Scale |
|--|---------------|-----------|-------------------|
| Ethnicity | EMR | Covariate | Categorical |
| Age and gender | EMR | Covariate | Categorical |
| BMI | EMR | Covariate | Categorical |
| Primary admission diagnosis | EMR | Covariate | Categorical |
| Secondary diagnoses | EMR | Covariate | Categorical |
| Passes with 21-g needle | In-person CRF | Covariate | Continuous |
| Passes with 19-g needle | In-person CRF | Covariate | Continuous |
| Total lymph nodes sampled | In-person CRF | Covariate | Continuous |
| Total sample yield 19-g | In-person CRF | Outcome | Continuous |
| Total sample yield 21-g | In-person CRF | Outcome | Continuous |
| Number of adequate samples by rapid onsite evaluation (ROSE) | In-person CRF | Outcome | Continuous |

| | | | |
|---|-------------------|-----------|-------------|
| Adequacy for molecular testing for lung cancer | In-person CRF | Outcome | Binary |
| Follow-up procedures required | EMR | Outcome | Categorical |
| Complications (hypotension, hypoxia, bleeding, other) | In-person CRF/EMR | Outcome | Categorical |

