| Total time sedated for procedure | In-person CRF/EMR | Covariate | Continuous |

f. Statistical analysis plan:

As each needle will be used for every lymph node evaluated, we will assume a paired data structure for analytic strategies. First, demographics and relevant patient factors in the study sample will be summarized using descriptive statistics. Bivariate comparisons (by needle gauge) will be conducted using McNemar tests, paired t-tests, or alternatives appropriate for paired data as dictated by the nature of each variable. If more flexibility is required (e.g., covariates for adjustment, specific correlation structure, random intercepts/slopes for patient clustering), we will specify linear mixed effects regression models to evaluate yield by needle gauge. For secondary aims (complications, etc.) we will employ descriptive analyses – no formal hypotheses will be tested.

g. Power analysis:

Assuming 85 paired samples (50 patients * 1.7 lymph nodes), a one-sided $\alpha=0.05$, and a standard deviation in yield of 10%, we expect 80% power to detect a mean difference of 2.7%. Given our anticipated yields of 83% (21g) and 90% (19g; 7% increase), we expect sufficient power to detect a statistically significant difference in average yield by needle gauge.

h. Strengths and Limitations:

Strengths of the study include:

- All physicians who perform the EBUS-TBNA procedure at Regions Hospital are investigators on this study, therefore we anticipate being able to approach all qualifying patients for enrollment.
- Both needle sizes are currently used as standard of care, based on physician discretion. Use of these needles in the study is not far from the current standard of care and could inform a more standardized methodology for needle size in the future

Limitations of the study include:

- Providers will not be blinded to needle gauge
- Difficult to attribute complications to a single needle gauge, given both will be administered
- As described above, procedural variation depends on physician judgment, which could bias results if judgment is differential with respect to needle gauge and/or yield

5. Setting/Environment/Organizational feasibility

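### The 80% power for a 2.7-point difference in section 4.g rests on an unsourced 10% SD that is impossible if yield is binary per node and unsupported if yield is the share of correct passes

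*Combined protocol and SAP*

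**What the plan says.** Section 2 defines the primary outcome as "19-gauge needle yield vs 21-gauge needle yield (true positive + true negative)/total" and does not say whether the total counts passes, nodes or patients. It hypothesises a gain of at least 7 points over a current 83%.

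The variable table in section 4.e has the row "Total sample yield 19-g | In-person CRF | Outcome | Continuous" (and a matching row for the 21-g needle), while another outcome in the same table reads "Adequacy for molecular testing for lung cancer | In-person CRF | Outcome | Binary".

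For comparisons by gauge in general, section 4.f offers "McNemar tests, paired t-tests, or alternatives appropriate for paired data as dictated by the nature of each variable". If more flexibility is needed, for example for adjustment or patient clustering, it adds that "we will specify linear mixed effects regression models to evaluate yield by needle gauge".

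Section 4.g takes 85 pairs (50 patients × 1.7 nodes), one-sided alpha 0.05 and "a standard deviation in yield of 10%, we expect 80% power to detect a mean difference of 2.7" percentage points. From this it concludes that power is sufficient for 83% versus 90%. It gives no source for the SD and does not say whether it belongs to one needle or to the paired difference.

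**The concern.** The SD is the only input to section 4.g that the reader cannot trace, and the whole power statement depends on it. With an SD of 10 points, power for a 7-point difference exceeds 99.9%, so the design appears to have a very wide margin. With 85 pairs, the largest SD of the difference that keeps 80% power at 7 points is 7 × √85 / 2.486 = 26.0 points. If the real SD is near or above that value, the margin is gone.

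This is the trial's only power figure and it concerns the primary outcome. If it is wrong, a null result could be read as ruling out a benefit that the trial had little chance of detecting.

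**Working it through.** **Inputs.** From section 4.g: n = 85 pairs, one-sided alpha 0.05, SD 10%, yields 83% and 90%. From section 4.a: "a minimum of 3 passes with each needle will be requested to provide adequate tissue for comparison". From section 4.d: "The average is 5.5 passes per lymph node" in standard practice, with 1 to 2 further passes per patient in the study. Pair discordance and within-node correlation are not given, so they are varied as assumptions. All figures treat the 85 pairs as independent.

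**1. The plan's figure.** Detectable difference = (1.645 + 0.842) × 10 / √85 = 2.70 points (2.72 with the t distribution). It reproduces if 10 is the SD of the paired difference. If 10 were each needle's SD, the SD of the difference would be 10 × √(2(1 − r)). The result is again 2.7 points at a between-needle correlation r = 0.5, but 3.8 points at r = 0.

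**2. Reading (a): correct or not, per node and needle.** The SD of the paired difference is √(ψ − d²), where ψ is the share of discordant nodes and d the difference.

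- Smallest possible ψ at d = 0.07 is 0.07: SD = √(0.07 − 0.0049) = 25.5 points.
- Independent needles: ψ = 0.90 × 0.17 + 0.83 × 0.10 = 0.236, SD = 48.1 points.
- Even at d = 0.027 the SD is at least √(0.027 − 0.000729) = 16.2 points.
- As a per-needle SD, 10% fails too: √(0.83 × 0.17) = 37.6 and √(0.90 × 0.10) = 30.0 points.

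One-sided McNemar power for 7 points, by enumerating the discordant counts:

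| Discordance ψ | Exact | Mid-p | Uncorrected |
|---|---|---|---|
| 7% (minimum) | 72% | 85% | 94% |
| 8% | 64% | 77% | 83% |
| 10% | 54% | 65% | 70% |
| 12% | 47% | 58% | 62% |
| 23.6% (independent) | 30% | 37% | 37% |

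The exact test never reaches 80%. The mid-p test does so only below 7.6% discordance, and the uncorrected test only below 8.3%. At 8.3%, nodes where only the 21-g needle is correct make up (0.083 − 0.07)/2 = 0.65%, or about half a node in 85. For 2.7 points (83% versus 85.7%, ψ from 2.7% to independence at 26.4%), power is 8–11% exact, 12–21% mid-p and 12–40% uncorrected.

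**3. Reading (b): share of correct passes, k per needle.** With independent passes the SD of the difference is √((0.83 × 0.17 + 0.90 × 0.10)/k) at 7 points. At 2.7 points the second term becomes 0.857 × 0.143. Paired t-test power:

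| k | SD at 7 points | Power, 7 points | Power, 2.7 points |
|---|---|---|---|
| 3 | 27.8 | 75% | 21% |
| 4 | 24.0 | 85% | 25% |
| 5 | 21.5 | 91% | 28% |
| 6 | 19.6 | 95% | 32% |

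The pass counts in section 4.d imply k from (5.5 + 1/1.7)/2 = 3.04 to (5.5 + 2/1.7)/2 = 3.34. Power is then 75.1% to 78.5% at 7 points and 21.0% to 22.2% at 2.7.

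**4. What a 10-point SD would need on reading (b).** At 2.7 points, a node effect shared by both needles would have to explain 1 − 0.01k/0.2637 of the pass variance: 89% at k = 3, 77% at k = 6. At 7 points there is a floor of √(d(1/k − d)) with equal passes: 13.6 points at k = 3, 11.2 at k = 4, 9.5 at k = 5. An SD of 10 is therefore out of reach at 7 points with 3 or 4 passes per needle, and possible only from about 5.

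**5. Sensitivity of reading (b) to correlation.** Take k = 3, correlation among passes in a node of 0 to 0.8, and correlation of the node effect between needles of 0 to 0.9 (all assumed). The SD then runs from 19.5 to 44.8 points, and normal-approximation power at 7 points from 95% down to 42%.

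**The case against.** The strongest reply is that the plan's own labels point away from the binary reading. Yield is listed as continuous where molecular adequacy is listed as binary, section 4.g speaks of a mean difference, and McNemar is offered for comparisons in general rather than assigned to yield. On the continuous reading the 7-point claim may hold, and 7 points is the hypothesis; 2.7 is only a detectable difference.

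Much of this is fair. The label does lean towards a continuous quantity, and power at 7 points could exceed 80% on that reading. But the label does not say what is counted. The section 2 formula is an accuracy proportion, section 4.g makes the node the pair, and section 4.c.iv describes recording the number of passes with each needle but no diagnosis per pass. The binary reading therefore stays open. On the share-of-passes reading, the 10% SD still has no support, and the 2.7-point figure fails unless agreement within nodes is very strong. A per-patient share of nodes is a third possibility, but it would give 50 pairs rather than 85.

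It can also be said that the calculation for independent passes is itself an assumption, and that 83% may not be a per-pass yield. Both are true. The documents supply no correlation and no unit for the 83%, and the range in step 5 widens the doubt in both directions.

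Finally, section 4.f already allows for patient clustering, though only conditionally. That is a secondary matter and does not affect the point about the SD.

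**Conclusion.** The concern holds. The arithmetic in section 4.g is correct; the input is not supported. On a per-node binary outcome a 10% SD is impossible at 83% versus 90%, and the claim of sufficient power for 7 points fails unless the 21-g needle almost never succeeds where the 19-g fails. Exact McNemar power is 30% to 72% for discordance between its minimum and independence. On the share of correct passes, the stated 80% power at 2.7 points becomes 21% to 32% with 3 to 6 independent passes per needle. The 7-point claim may stand there, at 75% to 95%, or 42% to 95% at 3 passes once correlation is varied.

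These ranges rest on assumed discordance and correlation and on 85 independent pairs. That 10% is impossible on the binary reading needs only the two stated yields. The design is not shown to have the power it states, so this should be corrected before the power statement is relied on.

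**What to change.** In sections 2 and 4.e, state the unit and scale of primary yield, including what the total counts, and bring section 4.f into line by naming the primary test for it. The choice of scale is the sponsor's.

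In section 4.g, remove the 10% SD and the 2.7% figure and give a calculation on the chosen scale:

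- **Binary per node:** a paired-binary (McNemar) calculation for 85 pairs at 83% versus 90% over a stated range of discordance, naming the test version. Withdraw or qualify the sentence on sufficient power.
- **Share of passes:** an SD derived from the expected passes per needle and stated correlations within nodes and between needles, with power restated at 7 points.

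As secondary additions, state outright that nodes cluster within patients and that the primary analysis will account for it, where section 4.f now leaves this conditional, and report the difference with a confidence interval.

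The cost is protocol and SAP wording. No patients or procedures are added, but the stated power will be less favourable.

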After initial discussion of the procedure (standard of care), the investigator will describe the option to participate in the study as part of the procedure. The consent will be provided and reviewed with the patient/family, explaining the study verbally. The patient undergoing the procedure will provide consent for him- or herself and will be given sufficient time to privately review the consent form and discuss potential involvement in the study with any family members or LAR, as applicable. The investigator will again meet with the patient to address any questions and discuss enrollment. If appropriate, the investigator will obtain consent from the patient and begin the study procedures.
 - iv. Data Sources:

Data will be obtained before, during, and after the procedure. Demographic data will be obtained prior to the procedure via EMR. Number of passes with each size needle will be recorded in-person following each procedure. Diagnosis yield and adequacy for molecular testing will be obtained following the procedure, from the investigator performing the procedure and from pathology lab analysis as recorded in the EMR and communicated to the investigator per standard practice for this procedure. Complications will be assessed in-person during the procedure and following the procedure via review of the patient's EMR 24± hours after the procedure.
- d. Interventions, treatments

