All reports and study materials will be identified only by a subject identification number to maintain subject confidentiality. Tissue samples obtained through the procedure will be identified as per standard procedure for Regions Hospital. These tissue samples will not be retained in any way outside of standard protocol and will not be labeled with the subject's study ID number. A master database linking the patient name & MRN will be maintained on a secure, password protected server in the CCRC. The CCRC uses a secure, electronic system that is currently used at Regions Hospital and is approved by IS&T Security. Any paper case report forms will be stored in locked file cabinets in the CCRC. The CCRC is a locked, protected department with limited badge access for security purposes.

8. Timeline

| | |
|---------------------------------------|-------------------------|
| Submission | April 2018 |
| Review and Approval | April-May 2018 |
| Training | May 2018 |
| Data Collection | June 2018-February 2019 |
| Data Analysis | March-April 2019 |
| Manuscript Preparation and Submission | May-June 2019 |

9. Dissemination/Sharing Results/Integration and Impact

We will submit results to an appropriate academic meeting, such as the Society for Critical Care Medicine and plan to publish the results in a journal targeting critical care medicine, i.e. Journal of Critical Care or Critical Care Medicine. We plan to disseminate results both throughout Regions and

the greater organization. This will include departmental and leadership meetings with the departments participating in this research.

10. References

1. Detterbeck, F.C., et al., *Executive Summary: Diagnosis and management of lung cancer, 3rd ed: American College of Chest Physicians evidence-based clinical practice guidelines*. Chest, 2013. **143**(5 Suppl): p. 7S-37S.
2. Wahidi, M.M., et al., *Technical Aspects of Endobronchial Ultrasound-Guided Transbronchial Needle Aspiration: CHEST Guideline and Expert Panel Report*. Chest, 2016. **149**(3): p. 816-35.
3. Hsu, L.H., et al., *Comparison of 19-gauge eXcelon and WANG MW-319 transbronchial aspiration needles*. Thorac Cancer, 2016. **7**(2): p. 264-70.
4. Biswas, A., et al., *Comparison of the yield of 19-G eXcelon core needle to a 21-G EBUS needle during endobronchial ultrasound guided transbronchial needle aspiration of mediastinal lymph nodes for the detection of granulomas in cases of suspected sarcoidosis*. J Thorac Dis, 2017. **9**(9): p. E864-E866.

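### The protocol names two different sources for the primary yield, relies in both on an operator who knows the needle, and does not mask the pathology reader to gauge

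*Combined protocol and SAP*

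**What the plan says.** Section 2 (Study Aims) gives the primary outcome as "19-gauge needle yield vs 21-gauge needle yield (true positive + true negative)/total". Section 4.a has both needles used in the same node: "For each lymph node sampled, we will alternate between the 19-g and the 21-g with each pass". It then promises that "Tissue obtained with the 19-g needles will be compared to tissue obtained with the 21-g needles with regards to diagnosis yield", and also with regard to adequacy for molecular testing.

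The source of the yield data is given twice, in different terms:

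- Section 4.c.iv (Data Sources) takes yield and molecular adequacy "from the investigator performing the procedure and from pathology lab analysis as recorded in the EMR".
- The variable table in Section 4.e has "Total sample yield 19-g | In-person CRF | Outcome | Continuous", with a matching row for 21-g. Neither row names the EMR or pathology. Molecular adequacy is likewise sourced to the in-person CRF, in a single row that is not split by gauge.

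Section 5 has research staff collect the completed paperwork from the investigator. Section 4.d states that investigators are not blinded, and Section 4.h lists as a limitation that "Providers will not be blinded to needle gauge". On specimens, Section 7 (Data Confidentiality and Privacy) says "Tissue samples obtained through the procedure will be identified as per standard procedure for Regions Hospital" and that they "will not be labeled with the subject's study ID number".

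**The concern.** Whether a sample is adequate, and what it shows, involves judgement. In this plan the person who may supply or record that judgement performed the passes and knows which needle was used. The protocol itself states a belief, in Section 3, that the 19-g needle will improve yield. The hypothesis is directional and the power statement is one-sided, so a leaning toward 19-g pushes toward a positive finding.

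The operator cannot be masked, but the laboratory reader could be. The protocol does not say whether the reader will know the gauge, whether pathology will report by needle, or which source prevails when the CRF and the EMR differ. At stake is whether a difference of a few points in yield can be attributed to the needle.

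**Working it through.** **1. The sections side by side.**

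| Question | What the protocol gives |
|---|---|
| Who supplies yield? | 4.c.iv: the operator and pathology in the EMR. 4.e: in-person CRF only. |
| Does the operator know the gauge? | Yes (4.d, 4.h). |
| Is an expectation stated? | Yes, in favour of 19-g (Section 3). |
| Is the pathology reader masked? | Not addressed. |
| Is pathology reported per node and needle? | Not stated; presupposed by 4.a, the two yield rows in 4.e and the paired analysis in 4.f. |
| Is the bias disclosed? | In part. 4.h covers unblinded providers and procedural variation that depends on physician judgement, not the laboratory read. |

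**2. The plan's own figure.** Section 4.g uses 50 × 1.7 = 85 pairs, SD 10%, one-sided alpha 0.05 and 80% power. Detectable difference = (1.645 + 0.842) × 10 / √85 = 2.697 points. The stated 2.7% reproduces, with the 10% used as the SD of the paired difference.

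**3. Scale in nodes.** The hypothesised 7 points is 0.07 × 85 = 5.95 nodes. A net 1 point is 0.85 node and a net 3 points is 2.55 nodes. Assessment that tips one to three nodes toward 19-g is therefore not small against the target.

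**4. Illustration of assessment bias.** The bias b and the discordance below are assumptions, not document figures. There is no true difference, and assessment favours 19-g by b points.

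- *Plan's SD of 10%:* false-positive rate = Φ(b√85/10 − 1.645).
- *Yield scored yes/no per node, McNemar (normal approximation, clustering ignored):* 5% of nodes yield with 21-g only and (5 + b)% with 19-g only. With d = b/100 and p = 0.10 + d, the rate = Φ[(√85·d − 1.645√p)/√(p − d²)].

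| b (points) | SD 10% | McNemar |
|---|---|---|
| 0 | 5% | 5% |
| 1 | 23% | 8.6% |
| 2 | 58% | 13.3% |
| 3 | 87% | 18.9% |

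The columns differ because a yes/no difference per node is far more variable than the plan's 10 points. At b = 1 its SD is √(0.11 − 0.0001) = 0.33, or 33 points.

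**5. Illustration of mixing, only if it occurred.** If needle labels are swapped in a share m of pairs, a true 7 points becomes 7(1 − 2m), or 5.6 at m = 10%. If a share f of nodes is pooled and both needles are credited with the one result, it becomes 7(1 − f), or 3.5 at f = 50%. Both pull toward no difference. The documents give no value for m or f.

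**The case against.** A reader might infer from Section 7 that specimens are labelled by hospital routine alone, so that material from the two needles will be mixed. The documents do not support that. The sentence sits in a confidentiality section, between statements about subject identifiers, and hospital routine is not described. The by-needle comparison in 4.a, the separate yield rows in 4.e and the paired analysis in 4.f all presuppose tracking by needle. The checklist and data collection instruments mentioned in Section 5 may spell it out. What remains is that the mechanism is not written down.

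A reader might also infer that the operator alone decides yield, on the day. That too goes too far. Section 4.c.iv names pathology as a source, places collection after the procedure, and can be read as the operator passing on a laboratory result. The CRF entry in 4.e may name a form and not a time limit, and no laboratory turnaround is given. The mismatch between the two sections stands all the same, and neither reading masks the laboratory.

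The disclosure in 4.h counts for something, but it stops at the providers and offers no mitigation. The bias sizes above have no basis in the documents. Moreover, yield is true positives plus true negatives over the total, so calling a sample adequate does not by itself make it count as yield. The numbers show sensitivity and are not an estimate.

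**Conclusion.** The point holds for the source and reading of the primary outcome. Sections 4.c.iv and 4.e disagree, the operator is unblinded, an expectation favouring 19-g is on record, and no masking of the pathology reader is stated. The comparison is open to assessment bias; that bias will occur is not shown. Specimen separation is an unspecified safeguard and not a demonstrated fault.

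The size is unknown. On the assumptions above, a bias of 1 to 3 points would lift a 5% one-sided error rate to about 9% to 19% by McNemar. The 23% to 87% range depends on the plan's SD of 10% and should not be quoted without it. The power arithmetic in 4.g is right on its own inputs and is not in question here. This is a low-cost improvement that should be made; it does not invalidate the design.

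**What to change.** 1. Reconcile Sections 4.c.iv and 4.e. State that research staff take the primary yield and molecular adequacy, for each node and each needle, from the final laboratory report and not from the operator's CRF. Split the molecular adequacy row by gauge.
2. State that each needle's material from a node goes into its own container, marked with the node and a neutral code (A or B) beside the usual hospital identifiers. The research centre holds the code-to-gauge key, and the code should not map to the same gauge in every node. This is compatible with Section 7, because the code is not the study ID.
3. State that the laboratory reports per code without being told the gauge. If hospital routine already separates material by needle, say so; only the coding is then new.
4. Say that rapid onsite evaluation remains unmasked, and report it as such.

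Cost: on the planned numbers, 85 × 2 = 170 coded specimens, a key, and slightly more handling around a laboratory read that takes place anyway. The documents do not describe laboratory workload, so that cost is a judgement. Masking may be incomplete, since Section 3 notes that needle size can affect tissue quantity and aspirated blood, either of which may hint at the needle. The coding must be in place before a node is sampled, because material pooled at the bedside cannot be separated later. The source rule can be adopted at any time before the data are analysed.
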